### **8.3.10 Pregnancy**

All pregnancies and outcomes of pregnancy should be reported to the Sponsor, with the exception of any pregnancy that is discovered before the participant has received any study intervention.

If a pregnancy is reported, the Investigator should inform the Sponsor within 1 day (ie, immediately but no later than 24 hours of when he/she becomes aware of the pregnancy).

Abnormal pregnancy outcomes (eg, spontaneous abortion, fetal death, stillbirth, congenital anomalies, ectopic pregnancy) are considered SAEs.

#### **8.3.10.1 Maternal Exposure**

If a participant becomes pregnant during the course of the study, study intervention should be discontinued immediately.

Pregnancy itself is not regarded as an AE unless there is a suspicion that the study intervention under study may have interfered with the effectiveness of a contraceptive medication.

Congenital abnormalities/birth defects and spontaneous miscarriages should be reported and handled as SAEs. Elective abortions without complications should not be handled as AEs. The outcome of all pregnancies (spontaneous miscarriage, elective termination, ectopic pregnancy, normal birth or congenital abnormality) should be followed up and documented even if the participant was discontinued from the study.

If any pregnancy occurs in the course of the study, then the Investigator or other site personnel informs the appropriate Sponsor representatives within 1 day, ie, immediately but no later than 24 hours of when he or she becomes aware of it.

The designated Sponsor representative works with the Investigator to ensure that all relevant information is provided to the Sponsor Patient Safety data entry site within 1 or 5 calendar days for SAEs (see Section 8.3.9) and within 30 days for all other pregnancies.

The same timelines apply when outcome information is available.

#### **8.3.10.2 Paternal Exposure**

Male participants should refrain from fathering a child or donating sperm during the study and for 2 days after the last dose of acalabrutinib.

Pregnancy of a participant's partner is not considered to be an AE. However, the outcome of all pregnancies (spontaneous miscarriage, elective termination, ectopic pregnancy, normal birth, or congenital abnormality), occurring from the date of the first dose until 2 days after the last dose of acalabrutinib, should, if possible, be followed up and documented in the Pregnancy Report Form. Consent from the partner must be obtained before the Pregnancy Report Form is completed.

Where a report of pregnancy is received, prior to obtaining information about the pregnancy, the Investigator must obtain the consent of the participant's partner. The local study team should adopt the Master Pregnant Partner Form in line with local procedures/requirements and submit it to the relevant regulatory authority/IRB/ethics committee prior to use.

#### **8.3.11 Medication Error**

If a medication error occurs during the course of the study, the Investigator or other site personnel informs the appropriate AstraZeneca representatives within 1 day, ie, immediately but no later than 24 hours of when he or she becomes aware of it.

The designated Sponsor representative works with the Investigator to ensure that all relevant information is completed within 1 (Initial Fatal/Life-Threatening or follow up Fatal/Life-Threatening) or 5 (other serious initial and follow up) calendar days if there is an SAE associated with the medication error (see Section 8.3.11) and within 30 days for all other medication errors.

The definition of a Medication Error can be found in Appendix B.

#### **8.3.12 Adverse Events of Special Interest**

Adverse events of special interest are events of scientific and medical interest specific to the further understanding of the acalabrutinib safety profile and require close monitoring and

rapid communication by the Investigators to the Sponsor. An AESI can be serious or non-serious. All AESIs will be recorded in the eCRF. Serious AESIs will be recorded and reported as per Section 8.3.9.

The following events are AESIs for participants receiving acalabrutinib and must be reported to the Sponsor expeditiously (see Section 8.3.9 for reporting instructions), irrespective of regulatory seriousness criteria or causality:

- **Ventricular arrhythmias** (eg, ventricular extrasystoles, ventricular tachycardia, ventricular arrhythmia, ventricular fibrillation)

## 8.4 Overdose

For this study, any dose of study intervention greater than the dose that was intended to be given will be considered an overdose.

- An overdose with associated AEs is recorded as the AE diagnosis/symptoms on the relevant AE modules in the eCRF and on the Overdose eCRF module.
- An overdose without associated symptoms is only reported on the Overdose eCRF module.

If an overdose on an AstraZeneca study intervention occurs in the course of the study, the Investigator or other site personnel inform appropriate Sponsor representatives immediately, but **no later than 24 hours** of when he or she becomes aware of it.

The designated Sponsor representative works with the Investigator to ensure that all relevant information is provided to the Sponsor Patient Safety data entry site within 1 or 5 calendar days for overdoses associated with an SAE (see Section 8.3.9) and within 30 days for all other overdoses.

## 8.5 Human Biological Samples

Instructions for the collection and handling of biological samples will be provided in the study specific laboratory manual. Samples should be stored in a secure storage space with adequate measures to protect confidentiality. Refer to Appendix C for further details on handling of human biological samples.

Samples will be stored for a maximum of 15 years from the date of the issue of the CSR in line with consent and local requirements, after which they will be destroyed/repatriated.

- Pharmacokinetic samples will be disposed of after the Bioanalytical Report finalization or six months after issuance of the draft Bioanalytical Report (whichever is earlier), unless consented for future analyses.

- Pharmacokinetic samples may be disposed of or anonymised by pooling. Additional analyses may be conducted on the anonymized, pooled PK samples to further evaluate and validate the analytical method. Any results from such analyses may be reported separately from the CSR.

The timing of PK [REDACTED] sample collections should be aligned as closely as possible and will be prioritized over other blood samples being collected simultaneously, except in the case of an AE for which relevant assessment/blood sample collection will be prioritized.

### **8.5.1 Pharmacokinetics**

Blood samples will be collected for the measurement of plasma concentrations of acalabrutinib and its metabolite, ACP-5862, as specified in the SoA (Table 1). Briefly, blood samples will be collected at 3 separate study visits at pre-dose and 0.5, 1, 2, 4, 6, and 12 hours post-dose. The 12-hour post-dose sample will be collected immediately prior to administration of the subsequent dose. The PK samples will be collected as described in Table 4.

Samples may be collected at additional time points during the study if warranted and agreed upon between the Investigator and the Sponsor, eg, for safety reasons. The timing of sampling may be altered during the course of the study based on newly available data (eg, to obtain data closer to the time of peak or trough matrix concentrations) to ensure appropriate monitoring.

Samples collected for analyses of plasma concentration of acalabrutinib and ACP-5862 may also be used to evaluate safety or efficacy aspects related to concerns arising during or after the study.

Samples will be collected, labelled, stored, and shipped as detailed in the Laboratory Manual.

#### **8.5.1.1 Determination of Drug Concentration**

Samples for determination of drug concentration in plasma will be assayed by bioanalytical test sites operated by or on behalf of AstraZeneca, using an appropriately validated bioanalytical method. Full details of the analytical method used will be described in a separate Bioanalytical Report.

Incurred sample reproducibility analysis, if any, will be performed alongside the bioanalysis of the test samples. The results from the evaluation, if performed, will be reported in a separate Bioanalytical Report.

**8.5.2**

**8.5.3 Immunogenicity**

No antidrug antibody samples will be collected in this study.

**8.6**

**8.7 Optional Genomics Initiative Sample**

Optional Genomics Initiative research is not applicable to this study.

**8.8 Health Economics**

Health economics is not applicable to this study.

## 9 STATISTICAL CONSIDERATIONS

### 9.1 Statistical Hypotheses

The primary objective of the study is to characterize the PK of acalabrutinib and its active metabolite (ACP-5862) and assess the safety and tolerability of acalabrutinib suspension when coadministered with a PPI in participants with COVID-19. There is no formal hypothesis testing for safety and efficacy endpoints.

### 9.2 Sample Size Determination

A sample size of 16 evaluable participants with COVID-19 was chosen based on the desire to gain adequate information while exposing as few participants as possible to the study procedures and study intervention. Given the inherent variability in the COVID-19 patient population, broad inclusion and exclusion criteria, and possible variability in treatment duration and PPI usage, approximately 20 participants will be enrolled in the study in order to have at least 16 evaluable participants able to complete PK Visit 2 (allowing for ~25% dropout rate due to disease progression).

**Note:** “Enrolled” means a participant’s, or his/her legally acceptable representative’s, agreement to participate in a clinical study following completion of the informed consent process. Potential participants who are screened for the purpose of determining eligibility for the study but are not randomly assigned/assigned in the study, are considered “screen failures”, unless otherwise specified by the protocol.

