## Number of Participants

Approximately 20 participants will be enrolled to have at least 16 evaluable participants.

**Note:** “Enrolled” means a participant’s, or his/her legally acceptable representative’s, agreement to participate in a clinical study following completion of the informed consent process. Potential participants who are screened for the purpose of determining eligibility for the study but are not randomly assigned/assigned in the study, are considered “screen failures”, unless otherwise specified by the protocol.

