## 4 STUDY DESIGN

### 4.1 Overall Design

This is an open-label, multi-dose study to evaluate the PK, and safety and tolerability of acalabrutinib suspension, when coadministered with a PPI, in participants with confirmed SARS-CoV-2 infection requiring hospitalization due to respiratory failure (as defined in Section 8.1.1.1) attributable to COVID-19 pneumonia and who have an NG tube in place. Approximately 20 participants will be included to ensure at least 16 participants are evaluable. Participants are considered evaluable if they have an evaluable PK profile, ie: (1) complete PK Visit 2 assessments; (2) receive active treatment; and (3) do not have unavailable or incomplete data that may influence the PK analysis.

In addition to BSC, participants will receive acalabrutinib suspension (ie, acalabrutinib 100 mg suspension in COCA-COLA delivered via NG tube) bid for 14 days (a maximum of 28 doses). Best supportive care is per discretion of the Investigator and institutional guidelines. Standard NG tubes supplied by the hospital will be used. Nasogastric tube placement in the stomach will be confirmed by chest x-ray.

To assess the effect of PPIs, all participants must be receiving treatment with a PPI at the start of the study. Treatment with a PPI can begin at any time prior to enrollment, provided participants have received PPI treatment for at least 24 hours prior to the first dose of acalabrutinib suspension (Figure 1). Any PPI is permitted, provided it meets the minimum equivalent daily dose of 20 mg rabeprazole (Appendix H). Participants must be on this dosage

of PPI at the start of the study. They may be weaned off PPIs during the study if medically appropriate.

Blood samples for plasma PK assessment of acalabrutinib and its metabolite (ACP-5862) will be collected at pre-dose and 0.5, 1, 2, 4, 6, and 12 hours following treatment with acalabrutinib suspension as described in Table 4 below and illustrated in Figure 1. Note that the sample at 12 hours must be collected prior to the subsequent acalabrutinib dose (for trough PK sample).

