## **5.4 Screen Failures**

Screen failures are defined as participants who consent to participate in the clinical study but are not subsequently entered in the study. A minimal set of screen failure information is required to ensure transparent reporting of screen failure participants to meet the Consolidated Standards of Reporting Trials publishing requirements and to respond to queries from regulatory authorities. Minimal information includes demography, screen failure details, eligibility criteria, and any SAE unrelated to the disease under investigation.

Individuals who do not meet the criteria for participation in this study (screen failure) may be rescreened. Rescreened participants should be assigned the same participant number as for the initial screening.

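### Section 9.2's figures do not agree: 20 participants with about 25% dropout leave 15 evaluable, not at least 16

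*Protocol*

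**What the plan says.** Section 9.2 puts the size justification in one sentence: "approximately 20 participants will be enrolled in the study in order to have at least 16 evaluable participants able to complete PK Visit 2", followed in brackets by "allowing for ~25% dropout rate due to disease progression". The target itself is a judgement, not a power or precision calculation: "A sample size of 16 evaluable participants with COVID-19 was chosen based on the desire to gain adequate information", weighed against exposing as few people as possible.

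Section 4.1 repeats the numbers without the dropout rate and in firmer terms: "Approximately 20 participants will be included to ensure at least 16 participants are evaluable". The synopsis (Section 1.1) gives the same 20 and 16 under Overall Design and under Number of Participants. Section 4.1 also says what evaluable means: "Participants are considered evaluable if they have an evaluable PK profile, ie: (1) complete PK Visit 2 assessments", plus having received active treatment and having no data gap that could affect the PK analysis.

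A note in Section 9.2, also in the synopsis, defines *enrolled* as "agreement to participate in a clinical study following completion of the informed consent process".

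**The concern.** The protocol gives a starting number, a loss rate and a finishing number. Any two of these fix the third, and here the third does not match. A plan that loses a quarter of 20 people keeps 15, yet the text promises at least 16, and Section 4.1 says the 20 are there to ensure it.

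No power calculation stands behind the study, and Section 9.4.2 rules out formal testing of the PK parameters. At least 16 evaluable at PK Visit 2 is therefore the only quantitative statement about size, and it serves a primary PK objective. If it cannot be derived from its own inputs, a reader of the study report cannot tell whether 15 evaluable participants would be the planned result or a shortfall.

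**Working it through.** **Inputs (all from Section 9.2)**
- Target evaluable at PK Visit 2: 16 or more.
- Planned number: about 20.
- Dropout: d, about 25%, so the retained fraction is 1 − d = 0.75.

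**Reproducing the stated 20**
- Target × (1 + d) = 16 × 1.25 = 20. This gives the protocol's figure exactly. It treats the 4 extra participants as 25% of the 16 (4/16 = 0.25), whereas dropout is lost from the number who start.

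**Correct inflation**
- Target / (1 − d) = 16 / 0.75 = 21.33, rounded up to 22.
- Check: 22 × 0.75 = 16.5 expected evaluable.

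**Forward check on the stated 20**
- 20 × 0.75 = 15 expected evaluable, one below the target.
- Loss that takes 20 to 16: 1 − 16/20 = 0.20, that is 20%.

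**Chance of reaching 16**

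Assume each of n dosed participants is evaluable independently with probability p = 1 − d. Then P(at least 16) is the sum over k = 16 to n of C(n, k) pᵏ (1 − p)ⁿ⁻ᵏ.

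For n = 20 and p = 0.75, the terms for k = 16 to 20 are 0.1897 + 0.1339 + 0.0669 + 0.0211 + 0.0032, which sum to about 0.415.

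| Dosed | Loss | Expected evaluable | P(at least 16) |
|---|---|---|---|
| 20 | 25% | 15.0 | 0.41 |
| 20 | 20% | 16.0 | 0.63 |
| 22 | 25% | 16.5 | 0.70 |

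At the stated rate, 20 participants are more likely to miss 16 than to reach it. Even where the averages agree (20 at 20% loss, or 22 at 25%), the chance of falling short is 0.37 or 0.30. None of these numbers ensures 16.

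**The case against.** The strongest reply is that this is a rounding matter with no consequence. Both the 20 and the 25% are marked as approximate, the gap is one participant, and 20 is two below the correct 22. Sections 9.1 and 9.4.2 plan no formal testing, so 15 in place of 16 changes no decision rule and no error rate.

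The effect on the primary analysis is also limited. The PK Analysis Set in Table 9 takes anyone with at least one dose and one usable post-dose acalabrutinib measurement, and PK Visit 1 is on Day 1. Someone lost before PK Visit 2 can therefore still contribute PK data. All of this stands, and it sets the severity. It does not make the three figures agree, and approximate inputs cannot support a promise to ensure a minimum.

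A reader might go further and infer that the 20 includes people who consent and then fail screening. The note defines *enrolled* by consent, and Section 5.4 says: "Screen failures are defined as participants who consent to participate in the clinical study but are not subsequently entered in the study". The protocol as a whole does not support that reading:
- The note's next sentence gives people who are screened "but are not randomly assigned/assigned in the study, are considered “screen failures”, unless otherwise specified by the protocol", which sets them apart.
- Sections 1.1 and 4.1 speak of participants being included.
- Appendix A 3 requires consent to come before enrolment.
- Inclusion criteria 4 to 6 treat enrolment as a later time point.
- Section 6.2.2 allows study drug only for those enrolled.

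The note's definition fits poorly with these places and deserves tidying, but it does not show that the 20 is diluted by screen failures. The protocol gives no screen-failure rate from which a further shortfall could be calculated.

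A reader might also infer that two more participants must be recruited. That does not follow. The 16 has no precision basis, the protocol wants as few people exposed as possible, and 22 would still miss 16 about 30% of the time.

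**Conclusion.** The statement is wrong as written, and the error is minor. With 20 participants and 25% loss the expected evaluable number is 15, and the stated 20 comes out only if the dropout rate is added to the target. The figures agree at 20% loss.

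The expected counts need no assumption beyond the protocol's own numbers. The probabilities (0.41 at 25% loss, 0.63 at 20%) assume that the stated rate is exact, that losses are independent, and that the 20 are all dosed.

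The finding concerns the PK Visit 2 evaluable count. It does not show that the PK, safety or efficacy summaries are invalid or that the study is too small for its descriptive purpose.

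**What to change.** In Section 9.2, restate the figures so that they agree, choosing whichever reflects the real expectation:
- about 20 participants dosed, giving about 15 evaluable at about 25% dropout; or
- about 20 participants dosed, giving about 16 evaluable at about 20% dropout.

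Carry the chosen statement into Section 1.1 (Overall Design and Number of Participants) and Section 4.1, and remove the promise there to ensure a minimum of 16.

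As a small clarification in the same edit, express the 20 as participants dosed, and amend the note on *enrolled* so that it fits the way the rest of the protocol uses the term.

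The cost is a few lines of protocol wording. No extra participants are needed and no analysis changes. Under the first option the stated evaluable number becomes one lower; under the second the stated dropout allowance becomes smaller.

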### 9.3 Populations for Analyses

The analysis populations are defined in Table 9.

**Table 9 Populations for Analysis**

Population/Analysis set	Description
PK Analysis Set	The PK Analysis Set will include all participants who received $\geq 1$ dose of acalabrutinib and had $\geq 1$ post-dose evaluable PK data point for acalabrutinib. The population will be defined by AstraZeneca, the pharmacokineticist, and the statistician prior to any analyses being performed.
Safety Analysis Set	The Safety Analysis Set will include all participants who received $\geq 1$ dose of study intervention
Efficacy Evaluable Set	The Efficacy Evaluable Set will include all participants who received $\geq 1$ dose of study intervention

ITT = intent to treat; PK = pharmacokinetic; PPI = proton-pump inhibitor.

## 9.4 Statistical Analyses

The SAP will be finalized prior to database lock and will include a more technical and detailed description of the statistical analyses described in this section. This section summarizes the planned statistical analyses of the most important endpoints, including primary and key secondary endpoints. Additional statistical analyses other than those described in this section may be performed if deemed appropriate.

### 9.4.1 General Considerations

For efficacy continuous endpoints, the baseline is defined as the last observation prior to the first dose of acalabrutinib suspension.

No missing data imputation will be applied for efficacy analysis.

For safety analysis, where individual data points are missing because of dropouts or other reasons, the data will be summarized based on reduced denominators.

Sensitivity analysis may be done by excluding participants with significant protocol deviations as appropriate.

### 9.4.2 Pharmacokinetic Analysis

A listing of PK blood sample collection times as well as derived sampling time deviations will be provided. Plasma acalabrutinib and ACP-5862 concentrations and PK parameters listed below will be summarized using appropriate descriptive statistics, which will be fully outlined in the SAP.

- Primary PK parameters:  $AUC_{12h}$ ,  $AUC_{last}$ , and  $C_{max}$ .
- Secondary PK parameters:
  - Acalabrutinib and ACP-5862:  $t_{1/2}$ ,  $t_{max}$ , and  $\lambda_z$ .
  - Acalabrutinib:  $CL/F$  and  $V_z/F$ .
  - Metabolite to parent ratio for  $C_{max}$ ,  $AUC_{last}$ , and  $AUC_{12h}$ .

No formal statistical test will be conducted for the PK parameters.

### 9.4.3 Safety Analysis

Safety assessments will consist of monitoring and recording of all AEs, SAEs, and AEs leading to discontinuation of study intervention, measurement of protocol-specified vital signs, ECG, laboratory variables, and other protocol-specified safety tests or measurements. All safety analyses will be performed on the Safety Analysis Set as defined in Section 9.3.

Verbatim descriptions of AEs will be mapped per the most recent version of MedDRA terms

and graded per NCI CTCAE, v5.0 or higher. Extent of exposure to study intervention, all AEs, SAEs, any AEs leading to study intervention discontinuation, and study intervention related AEs will be summarized. The frequency of AEs will be summarized by system organ class and preferred term per MedDRA and by the worst reported NCI CTCAE grade. Treatment-emergent AEs will be summarized, unless otherwise specified. Treatment-emergent AEs are defined as AEs starting or ongoing AEs worsening after the first dose of study intervention and AEs with start date up to the last dose of study intervention plus 28 ( $\pm$  3) days.

Laboratory abnormalities will be defined based on laboratory normal ranges (universal normal ranges, if central laboratory). Selected laboratory parameters may be analyzed with shift tables and summaries of changes from baseline to worst post-treatment value.

Vital sign and all other safety assessments will be tabulated and summarized.

Full details of AE, laboratory assessments, vital sign assessments, and all other safety assessments will be provided in the SAP.

